4.2 Dose Limiting Toxicity

For the purposes of safety management and defining DLTs, the combination of MGA271 and pembrolizumab, or the combination of MGA271+MGA012 will be treated as one entity. If a DLT is considered related to study drug, no distinction will be made as to which agent is the causative agent and administration of both agents will be stopped. One exception to this rule will be in the circumstance in which a DLT occurs during or immediately following the first pembrolizumab infusion or MGA012 infusion and before the first MGA271 administration. In this case, the toxicity will be attributed to pembrolizumab or MGA012 alone and will not count as a DLT of the combination of study drugs; in this case the patient will be replaced by another patient in the dose cohort.

In general, for patients who experience an AE that may meet the criteria for a DLT, subsequent administration of the study drugs should be held pending management and/or resolution of the event and assessment of attribution to the study drugs. Criteria for subsequent continuation of therapy are outlined below. No dose reductions of either MGA271 or pembrolizumab or MGA012 are allowed during the study.

Dose limiting toxicities will be based on treatment-emergent drug-related AEs (or laboratory abnormalities) occurring during the DLT Evaluation Period (defined as the time following administration of the first dose of pembrolizumab to the day of the third planned administration of pembrolizumab [i.e., Cycle 1/Initial Tumor Assessment Cycle.]) The severity of AEs will be graded according to the National Cancer Institute (NCI) Common Terminology Criteria for Adverse Events (CTCAE) version 4.03.

Dose limiting toxicities are defined separately for hematologic and non-hematologic events as outlined below.

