4.2.3 Hepatic Non-Hematologic Dose Limiting Toxicity

- AST or ALT $> 5 \times$ ULN or total bilirubin $> 3 \times$ ULN
 - For patients with liver metastasis who begin treatment with Grade 2 AST or ALT, if the AST or ALT increases by $\geq 50\%$, relative to baseline and lasts for at least 1 week.
 - Please see **Section 6.5.2.2** for further management guidelines.
- Any event meeting the criteria for Hy's law as follows (all three features):
 - Aspartate aminotransferase (AST) and/or alanine aminotransferase (ALT) $> 3 \times$ ULN.
 - Concurrent elevation of total bilirubin $> 2 \times$ ULN without initial evidence of cholestasis.
 - No alternative etiology can be identified.

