4.4 Rules for Continuation of Study Therapy

Patients who tolerate treatment with pembrolizumab and MGA271, or who tolerate treatment with MGA271+MGA012, may continue to receive additional treatment with the study drugs as specified in the protocol (see [Section 4.1.1](#)), until any one of the following conditions are met:

- After documentation of a confirmed complete response (cCR), MGA271 and pembrolizumab, or MGA271+MGA012, are continued for one more Tumor Assessment Cycle
- Patient meets criteria for immune-related disease progression (irPD) ([Appendix 6](#))
- Occurrence of drug-related DLT as defined for the DLT Evaluation Period
- The Sponsor, Investigator, or Regulatory Agency terminates the study
- Withdrawal of patient due to an AE or SAE
- Withdrawal of patient consent
- Completion of protocol defined therapy

- Investigator discretion
- Pregnancy
- Death

Note: For individual patients who meet these criteria, but are otherwise considered to be experiencing clinical benefit by the investigator, consideration may be given to extension of therapy on a case-by-case basis in consultation with the Sponsor. If a patient completes 6 cycles of therapy and is experiencing clinical benefit as determined by the investigator, consideration may be given to extension of therapy for an unrestricted number of additional 9-week treatment cycles of MGA271 and pembrolizumab or MGA271+MGA012 on a case-by-case basis in consultation with the Sponsor. Assessments and procedures for Cycles 7 and beyond will be done according to those for Cycle 6 (see [Appendix 1](#)). Such unrestricted treatment may continue until the patient either 1) meets the criteria for permanent discontinuation (see [Section 5.3.1](#)), or 2) a rollover protocol becomes available.

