4.5 Guidelines for Dose Modification

No intra-patient dose escalation will be allowed. No dose reductions will be allowed with exception of 1) reduction of infusion rate during re-challenge for patients experiencing an infusion reaction ([Section 6.5.1](#)) or 2) reduction of dose in patients receiving MGA271 at a dose that is subsequently determined to exceed the MTD ([Section 4.3](#)). For patients who experience DLT that is considered related to either study drug, no further pembrolizumab or MGA271 or MGA012 will be administered.

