4.5.1 Dose Delays

Patients who experience toxicity that is potentially dose-limiting should have study drug held pending assessment, management and resolution of the toxicity. For patients in whom the toxicity is assessed to be unrelated to study drug or for whom the toxicity does not meet the criteria for DLT, therapy may be re-instituted at the same dose and schedule that was administered prior to the event, presuming the toxicity has resolved to \leq Grade 1 in severity. Reinstitution of therapy shall be conducted as follows:

For patients in whom the toxicity is assessed to be related to study drug, dose interruptions of up to 14 days are allowed for drug related toxicity. This may include up to one missed dose of pembrolizumab and up to 2 consecutively missed doses of MGA271. For the MGA271+MGA012 combination, Cohort 4, this would allow for a maximum of one dose each of MGA271 and MGA012. The procedures at the original scheduled missed visit should be performed as soon as possible with treatment reinstated as if no delay had occurred, picking up at the day where the interruption occurred, and patients receive the full complement of pembrolizumab and MGA271 or MGA271+MGA012 or as outlined in The Time and Event Schedule ([Appendix 1](#)). Patients with infusion delays $>$ 14 days due to drug related toxicity will discontinue both study drugs, complete the End of Treatment visit, and then enter the Efficacy Follow-up Period.

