6.5.2.2 Hepatic Toxicity

6.5.2.2.1 Elevations in Transaminases

Section 2.3.2.1 provides a summary of the pembrolizumab safety profile. Management guidelines for patients experiencing hepatic toxicity are as follows:

Grade 1 elevations

- No specific therapy required

Grade 2 elevations

- For elevations in transaminases 3 to $5 \times$ ULN (Grade 2), rule out viral and other etiologies, consider immediate oral steroids such as prednisone 60 mg /day divided twice daily, and hold MGA271 and pembrolizumab or MGA012.
- If improvement to \leq Grade 1 does not occur within 48 hours with oral steroids, consider IV steroids such as methylprednisolone at 2 mg/kg/day divided twice daily or oral steroids such as prednisone 60 to 120 mg per day, divided twice daily
- Resume pembrolizumab or MGA012, and/or MGA271, at next scheduled dose if:
- No more than one dose of pembrolizumab or MGA012 was missed and no more than 2 doses of MGA271 were missed
- If improvement to \leq Grade 1 does not occur within 14 days discontinue pembrolizumab or MGA012, and MGA271

Grade 3 elevations

- Permanently discontinue MGA271 and pembrolizumab or MGA012, for AST or ALT greater than 5 times ULN unless patient has liver metastasis and began treatment with Grade 2 AST or ALT
- For patients with liver metastasis who begin treatment with Grade 2 AST or ALT, permanently discontinue if AST or ALT increases by greater than or equal to 50% relative to baseline and lasts for at least 1 week
- Initiate IV steroids; suggest methylprednisolone at a dosage of 2 mg/kg/day divided twice daily.
- If no response to corticosteroid therapy within 3 to 5 days is observed, consider adding immune suppression therapy with mycophenolate. Infliximab is not recommended because of a potential for autoimmune hepatitis (30).
- Monitor liver function testing at least twice weekly (or more frequently as clinically appropriate in the judgment of the investigator) until transaminases have returned to Grade 1 or baseline.

Grade 4 elevations

- Discontinue pembrolizumab or MGA012, and MGA271
- Treat as for Grade 3 elevation

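### The hepatic management guideline omits Hy's law, so its Grade 2 transaminase rule tells sites to resume dosing where Section 4 ends it

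*Protocol*

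**What the plan says.** **Definition.** Protocol Section 4.2.3 has four hepatic DLT criteria: AST or ALT above 5 x ULN; total bilirubin above 3 x ULN; a rise of at least 50% lasting at least a week in patients with liver metastasis who started with Grade 2 AST or ALT; and Hy's law. The last has its own bullet, beginning "Any event meeting the criteria for Hy's law as follows (all three features". The features are AST and/or ALT above 3 x ULN, concurrent bilirubin above 2 x ULN without initial cholestasis, and no alternative cause.

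**Consequence.** Four clauses end treatment after a related DLT.
- Section 4.2: "no distinction will be made as to which agent is the causative agent and administration of both agents will be stopped".
- Section 4.4 lists "Occurrence of drug-related DLT as defined for the DLT Evaluation Period" as a stopping condition. Its Note adds that, for patients judged to be benefiting, "consideration may be given to extension of therapy on a case-by-case basis in consultation with the Sponsor".
- Section 4.5: "For patients who experience DLT that is considered related to either study drug, no further pembrolizumab or MGA271 or MGA012 will be administered".
- Section 4.5.1 allows restart only when the toxicity is unrelated "or for whom the toxicity does not meet the criteria for DLT, therapy may be re-instituted at the same dose and schedule", and only once it is Grade 1 or lower.

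**Hepatic guideline.** Section 6.5.2.2.1, Grade 3: "Permanently discontinue MGA271 and pembrolizumab or MGA012, for AST or ALT greater than 5 times ULN", with a separate 50% rule for patients with liver metastasis who began at Grade 2. For Grade 2 (3 to 5 x ULN) the site rules out other causes, considers steroids and holds both drugs. Then: "Resume pembrolizumab or MGA012, and/or MGA271, at next scheduled dose if". The one condition listed under that line is that at most one anti-PD-1 dose and two MGA271 doses were missed. Failure to reach Grade 1 within 14 days means discontinuation. Section 6.5.2.2.2 stops both drugs for bilirubin above 3 x ULN. Its Grade 2 rule holds them until improvement, with the same 14-day limit and no resume line.

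**Elsewhere.** Section 4.2.2 and the synopsis also place Hy's law in a list of events that may, rather than will, count as DLTs. Section 7.8.2.6 makes Hy's law values reportable within 24 hours and says that study drug may be stopped if the event is related.

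**The concern.** Section 6.5.2.2 is where a site looks when transaminases rise. It repeats every hepatic DLT criterion as a permanent stop except the one that combines moderate elevations of both measures. It asks for an etiology work-up but does not say what follows when no other cause is found, which is exactly the Hy's law case.

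This looks like an omission rather than a choice. Inclusion criterion 15 excludes patients whose earlier checkpoint-inhibitor event met Hy's law even if it fully resolved, so the protocol already treats recovery as insufficient ground for re-exposure. Section 6.5.2 also presumes that signs of inflammation are drug related unless another cause is identified, so the 'unrelated' route to restart in Section 4.5.1 will seldom be open.

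At stake is the re-dosing of a patient with suspected drug-induced liver injury. No endpoint or analysis is affected.

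**Working it through.** The plan gives no figure on this point to reproduce. The check sets the rules side by side and then asks whether the guideline's own limits would block the resumption.

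**1. DLT criteria against guideline stops**

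| Criterion in 4.2.3 | Permanent stop in 6.5.2.2? |
|---|---|
| AST/ALT > 5 x ULN | Yes, 6.5.2.2.1 Grade 3 |
| Liver metastasis, Grade 2 at start, rise of at least 50% for at least 1 week | Yes, 6.5.2.2.1 Grade 3 |
| Bilirubin > 3 x ULN | Yes, 6.5.2.2.2 Grade 3 |
| Hy's law | No |

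Three of four are carried over.

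**2. Where the two sets of rules disagree.** Take a drug-related event with no cholestasis, no other cause, and no liver metastasis with Grade 2 AST or ALT at the start.
- DLT if AST/ALT > 5, or bilirubin > 3, or (AST/ALT > 3 and bilirubin > 2), all x ULN.
- Guideline stop if AST/ALT > 5 or bilirubin > 3.
- The difference is AST/ALT > 3 to 5 with bilirubin > 2 to 3.

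A grid in steps of 0.1 x ULN (AST/ALT 0.5 to 10, bilirubin 0.5 to 6) confirms this. The mismatch covers AST/ALT 3.1 to 5.0 (20 values) by bilirubin 2.1 to 3.0 (10 values), 20 x 10 = 200 cells. In all of them Hy's law is the only DLT criterion met.

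In patients with liver metastasis who start at Grade 2, the zone without a guideline stop runs to just under 1.5 x baseline. From a baseline of 4 x ULN that is 1.5 x 4 = 6 x ULN. Values above 5 fall under the Grade 3 heading, which has no resume line.

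**3. One patient, two answers.** ALT 4 x ULN, bilirubin 2.5 x ULN:
- Sections 4.2.3 and 4.5: DLT, no further drug.
- Section 4.5.1: not eligible to restart.
- Section 6.5.2.2.1: Grade 2; hold, then resume at the next scheduled dose.
- Section 6.5.2.2.2: below the > 3 x ULN stop; at most a hold until improvement.

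**4. Does the missed-dose limit block resumption in Cohort 4?** Inputs: a minimum of 18 days between doses (Sections 6.3.1 and 6.3.3), the 14-day recovery limit, and missed-dose limits of 1 (MGA012) and 2 (MGA271). Since 14 < 18, a recovery in time spans at most one dosing day. Missed doses are then at most 1 of each, and 1 ≤ 1 and 1 ≤ 2. The condition is always met, so every such patient who recovers to Grade 1 within 14 days qualifies to resume.

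**5. Ceiling on later exposure for one patient.** Planned maximum 17 doses of each drug. After the Day 1 dose, 17 − 1 = 16 remain; after the Day 22 dose, 17 − 2 = 15. Section 4.5 allows 0, apart from the 4.4 Note.

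**6. Who is affected.** The Efficacy paragraph under Section 2.3.1.1.2.1 says patients in the pembrolizumab cohorts have completed combination treatment. That leaves Cohort 4: up to 15 patients at a dose level, with more possible if the de-escalation levels in Section 4.1.2 are opened.

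**The case against.** The strongest reply is that Section 4 already decides the matter. Section 4.5 is mandatory, and Sections 4.2 and 4.5.1 hold drug while the event is assessed, so the DLT decision comes before any restart. Section 6.5.2 calls its contents general guidelines. The missed-dose and 14-day limits in Section 6.5.2.2.1 mirror those in Section 4.5.1, which suggests they were written for toxicity that is eligible to restart. The bilirubin subsection gives no resume instruction. The 24-hour report alerts the Sponsor, and Section 5.3.1 requires withdrawal when the investigator judges that continuing harms the patient. Nothing obliges Section 6.5.2 to repeat every DLT; the ocular DLT in Section 4.2.2 has no guideline there either.

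Much of this stands. Section 4 gives the right answer, a careful reader would reach it, and the reporting duty makes an unnoticed re-dose less likely.

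It does not remove the conflict. No clause ranks the sections, and Section 6.5.2.2 does not refer to 4.2.3, 4.5 or 4.5.1. The pointer from 4.2.3 to 6.5.2.2 sits under the AST/ALT/bilirubin bullet, not the Hy's law bullet. A hold until improvement does not forbid resumption. The report triggers notice, not a stop. The ocular case differs because the guideline is silent there, whereas for transaminases it gives a contrary instruction.

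The event may also be rare. The nearest figure is immune-mediated hepatitis with pembrolizumab in Section 2.3.2.1: 0.7% of 2799 patients, 0.1% at Grade 2. Assuming those rates, the chance of at least one case among 15 patients is 1 − 0.993^15 ≈ 10% or 1 − 0.999^15 ≈ 1.5%. This is a different anti-PD-1 antibody and a different event, so it is only a rough guide, and the conclusion does not rest on it.

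**Conclusion.** The conflict is real but narrow. For AST/ALT > 3 to 5 x ULN with bilirubin > 2 to 3 x ULN, drug-related and meeting the other Hy's law features, Section 6.5.2.2.1 gives a resume instruction that Sections 4.5 and 4.5.1 do not allow. It is a minor, nice-to-have correction with a safety rationale. It rests on minimum dose intervals being kept in Cohort 4 and on the stated completion of the pembrolizumab cohorts. Other Grade 2 elevations may properly resume.

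Three stronger readings are tempting, and the documents do not support them.
- A reader might infer that the permissive bullet in Section 4.2.2 makes the DLT count uncertain. It does not: Section 4.2.3 defines Hy's law as a DLT outright, and the Section 4.2.2 bullet itself points there.
- A reader might infer that the 4.4 Note is the only wording that leaves room for further dosing, and that the 4.2.2 bullet merely duplicates 4.2.3. Neither holds: Sections 4.2.2 and 7.8.2.6 are also permissive about this event, and the bullet differs in force from 4.2.3. That is why the correction must cover them.
- A reader might infer that patients are likely to be re-dosed. The mandatory text in Section 4 and the 24-hour report count against that, and no rate for this event is given. The 16 of 17 doses is a ceiling for one hypothetical patient, not a frequency.

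**What to change.** Make three linked edits.

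1. In Sections 6.5.2.2.1 and 6.5.2.2.2, ahead of the Grade 2 rules, add: *Drug-related events meeting Hy's law (Section 4.2.3): hold both drugs during the etiology work-up; if no alternative etiology is found, permanently discontinue MGA271 and pembrolizumab or MGA012 regardless of grade, per Sections 4.5 and 4.5.1; the Grade 2 resume rule does not apply.*
2. Delete the Hy's law bullet from the permissive DLT list in Section 4.2.2 and in the synopsis, so that Section 4.2.3 governs.
3. In Section 7.8.2.6, make the sentence that permits stopping drug for a related reportable event subject to Section 4.5.

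Edits 2 and 3 belong with edit 1; without them, permissive wording on the same event remains. The guideline would then match all four hepatic criteria and the zone above would close. The cost is one sentence in each hepatic subsection, one bullet removed in two places and one qualifier, with no added visits, data or patients and no change to the criteria in Section 4.2.3.

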6.5.2.2.2 Elevations in Total Bilirubin

Management guidelines for patients experiencing elevations in total bilirubin are as follows:

Grade 1 elevations

- No specific therapy required

Grade 2 elevations

- Hold MGA271 and pembrolizumab or MGA012, until improvement to \leq Grade 1
- Consider oral steroids
- If improvement to \leq Grade 1 does not occur within 14 days, discontinue MGA271 and pembrolizumab or MGA012, and begin oral steroids

Grade 3 elevations

- For elevations in total bilirubin $> 3 \times$ ULN, permanently discontinue MGA271 and pembrolizumab or MGA012, and
- Initiate IV steroids; suggest methylprednisolone at a dosage of 2 mg/kg/day divided twice daily.
- If no response to corticosteroid therapy within 3 to 5 days is observed, consider adding immune suppression therapy with mycophenolate. Infliximab is not recommended because of a potential for autoimmune hepatitis (30).
- Monitor liver function testing at least twice weekly (or more frequently as clinically appropriate in the judgment of the investigator) until transaminases have returned to Grade 1 or baseline.

Grade 4 elevations

- Discontinue pembrolizumab or MGA012, and MGA271
- Treat as for Grade 3 elevation

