As of 12 October 2018 (1), 133 patients have been treated in this study. Combination MGA271 and pembrolizumab dose escalation and expansion cohorts are closed to further enrollment; patients enrolled in these cohorts have completed combination treatment; no MTD was defined. The MGA271 + pembrolizumab combination treatment demonstrated an acceptable safety profile. In the anti-PD-1/PD-L1 naïve patients treated with MGA271 + pembrolizumab, the objective response rates benchmarked favorably with historical experience with anti-PD-1 monotherapy: SCCHN (post-platinum chemotherapy) was 33.3% and NSCLC (PD-L1 < 1%) was 35.7%; see **Table 1**.

Table 1 **Enoblituzumab (MGA271) + Pembrolizumab Combination Benchmarks Favorably**

SCCHN		Study Results			
Agent (Study)	Enoblituzumab + Pembrolizumab	Nivolumab (CM-141) ^(a)	Pembrolizumab (KN-012) ^(b)	Pembrolizumab (KN-040) ^(c)	
N	18	240	174	247	
ORR	33.3%	13%	16%	15%	
NSCLC					Study Results
Agent (Study)	Enoblituzumab + Pembrolizumab	Nivolumab (CM-057) ^(d)	Nivolumab (CM-017) ^(e)	Pembrolizumab (KN-001) ^(f)	
Histology	Both	Non-Squamous	Squamous	Both	
N	14	108	54	87	
ORR	35.7%	9%	17%	8%	

(a) Ferris, et al., 2016, *N Eng J Med*; (b) Keytruda® package insert; (c) Cohen, et al., 2017, ESMO LBA45; (d) Borghaei, et al., 2015, *NEJM*; (e) Brahmer, et al., 2015, *NEJM*; (f) Garon, et al., 2015, *NEJM*

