8.3 End of Treatment Visit

A list of evaluations to be performed for the End of Treatment visit is provided in [Appendix 1](#). Criteria for triggering the End of Treatment visit are specified in [Section 5.3](#). The End of Treatment Visit should be performed after the patient has met off-study criteria or has been followed for at least 28 days after the last dose of study drug depending on ability to follow the patient and duration and severity of ongoing AEs. It is recognized that certain patients (such as those experiencing progression of disease) may be cared for in facilities other than the participating investigational site, may proceed to receive other cancer therapy, and/or may elect not to return to the investigational site. Therefore, this visit is considered optional, but should be carried out whenever possible.

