2. B7-H3 expression are not required for eligibility in this study; however, tumor expression of B7-H3 will be evaluated for all patient tissue samples or slides for B7-H3 and tissue should be identified before initiating therapy, but do not need to be submitted or resulted in advance of initiating therapy and may be submitted by C1 D43. Patients should have a formalin-fixed, paraffin embedded (FFPE) tumor specimen or unstained slides identified for analysis, to enable determination of the expression of B7-H3 within tumor specimens using IHC staining. If an archived tumor specimen is not available, patients who undergo a fresh tumor biopsy ([Section 7.11.4.3](#)) can have B7-H3 expression evaluated from a FFPE sample obtained from the fresh tumor biopsy. In this case, the biopsy should be obtained prior to initiating study therapy. In cases in which an archived sample and fresh tumor sample are both available, B7-H3 expression can be confirmed with either FFPE sample.
3. MGA012 infusion on Days 1 and 22: ECGs will be obtained before both the MGA012 and MGA271 infusions, at the end of both MGA012 and MGA271 infusions. **C1D1:** 3 hours after start of MGA271 infusion. **C2 and beyond: D1** pre-infusion MGA012. If infusion is interrupted, ECGs will be done based on the time of re-starting infusion.
4. For women of childbearing potential, to be obtained within 72 hours prior to initial dose of MGA012.
5. Includes height (screening only) and weight. Note that full physical exams to be done on screening, Day 1 (baseline), and at the EOTV. All other physical exams will be directed physical exams based on patient symptoms, tumor location and as clinically indicated.
6. Samples will be drawn prior to infusion and analyzed by the LOCAL laboratory. Day 1 of Cycle 1 safety labs do not need to be repeated if done within 3 days of Day 1.
7. Includes ALB, ALK-P, ALT, AST, bicarbonate, BUN, Ca, Cl, creatinine, glucose, magnesium, phosphorus, K, Na, total protein, uric.
8. Includes amylase, total and direct bilirubin, lipase.
9. The 2 hour after start of MGA012 infusion and 3 hour after start of MGA271 infusion vital signs measurements may be deferred if continuing monitoring is not clinically indicated. If infusion is interrupted, vital signs will start from the beginning when infusion resumes.

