	C1D8, C2D8	No specific timepoint	No specific window

Table 9 Time Window Allowances for Study Evaluations and Procedures for MGA271 and MGA012 (Cohort 4 Only)

Procedure	Study Day	Time Point	Window Allowance
PK	C1D1, C1D22 C2D1, C2D22 C3 and beyond: D1 and D22	Pre-Infusion MGA012	Any time before dosing on visit day (dosing day) or day before
	C1D1, C1D22 C2D1, C2D22 C3 and beyond: D1 and D22	End of MGA012 infusion	-10 min to 0 min (EOI)
	C1D1, C1D22 C2D1, C2D22 C3 and beyond: D1 and D22	End of MGA271 Infusion	-10 min to 0 min (EOI)
	C1D1, C2D1	5 hours after Start of MGA271 Infusion	+/-30 min
	C1D2, C1D4, C1D8, C1D15	No specific timepoint	No specific window
	C2D2, C2D4, C2D8, C2D15	No specific timepoint	No specific window
Vital Signs	C1D1, C1D22	Pre-Infusion MGA012	-15 min to 0 min before SOI
		30 minutes after Start of MGA012 Infusion	+/-15 min
		End of Infusion (MGA012)	0 min to +15 min after EOI
		2 hours after Start of MGA012 Infusion	+/-15 min
	C1D1, C1D22	Pre-Infusion MGA271	-15 min to 0 min before SOI (Note: must be taken after post MGA012 vitals)
		60 minutes after Start of MGA271 Infusion	+/-15 min
		End of Infusion MGA271	0 min to +15 min
		3 hours after Start of MGA271 Infusion	+/-30 min
		Pre-Infusion MGA012	-15 min to 0 min before SOI
		30 minutes after Start of MGA012 Infusion	+/-15 min
		End of Infusion MGA012	0 min to +15 min after EOI

Table 9 Time Window Allowances for Study Evaluations and Procedures for MGA271 and MGA012 (Cohort 4 Only)

Procedure	Study Day	Time Point	Window Allowance
		2 hours after Start of MGA012 Infusion	+/-15 min
		Pre-Infusion MGA271	-15 min to 0 min before SOI (Note: must be taken after post MGA012 vitals)
		60 minutes after Start of MGA271 Infusion	+/-15 min
		End of Infusion MGA271	0 min to +15 min
		3 hours after Start of MGA271 Infusion	+/-30 min
ADA	Days 1 and 22 all Cycles	Pre-Infusion (MGA012)	Any time before dosing on visit day (dosing day) or day before
Physical Examination	C1: D1, 22, C2 and beyond: D1, 22, 43	Pre-Infusion	-3 to 0 days prior to dosing
Disease Assessment	C1: D42; C2 and beyond: D63	Pre-Infusion	-3 to 0 days prior to dosing
CBC with differential, platelet count	C1: D1, 22, C2 and beyond: D1, 22	Pre-Infusion	-3 to 0 days prior to dosing
Chemistry panel	C1: D1, 22, C2 and beyond: D1, 22	Pre-Infusion	-3 to 0 days prior to dosing
Special chemistry	C1: D1, 22, C2 and beyond: D1, 22	Pre-Infusion	-3 to 0 days prior to dosing

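### The Grade 3-4 bilirubin rule stops twice-weekly liver testing when transaminases recover, not when bilirubin recovers

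*Protocol*

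**What the plan says.** Protocol Section 6.5.2.2 handles hepatic toxicity in two parts: transaminases (6.5.2.2.1) and total bilirubin (6.5.2.2.2).

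In the bilirubin part, the Grade 3 block applies above 3 x ULN. Both drugs stop permanently, IV steroids start, and mycophenolate is considered ("If no response to corticosteroid therapy within 3 to 5 days is observed"). The last bullet says to "Monitor liver function testing at least twice weekly (or more frequently as clinically appropriate in the judgment of the investigator) until transaminases have returned" (target: Grade 1 or baseline). Grade 4 is to be treated as Grade 3, so it takes over the same bullet.

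The transaminase part ends its own twice-weekly testing with the same words, "until transaminases have returned to Grade 1 or baseline".

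The Grade 2 bilirubin rule is tied to the bilirubin elevation itself: "Hold MGA271 and pembrolizumab or MGA012, until improvement to" Grade 1 or lower.

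**The concern.** The bullet is triggered by one analyte and released by another. It matches the transaminase bullet word for word, which points to text carried over without adapting the end point.

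Two things are at stake for the patient: following the event until it resolves, and detecting later worsening, either from Grade 3 to Grade 4 or a subsequent ALT/AST rise toward Hy's law. The second depends on someone continuing to test.

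The point has some relevance to the Cohort 4 partner drug. Section 2.3.3.1.2 lists raised blood bilirubin among the most frequent events (at least 20%) with MGA012 500 mg Q4W, and reports one participant with a bilirubin-related immune event that did not resolve. The same section describes the frequent events as generally low-grade, so Grade 3-4 cases should be uncommon.

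**Working it through.** This is mainly a check of text; the plan gives no figure to reproduce.

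**1. Trigger against release**

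| Rule | Trigger | Released by |
|---|---|---|
| 6.5.2.2.1, Grade 3-4: twice-weekly tests | AST/ALT | AST/ALT at Grade 1 or baseline |
| 6.5.2.2.2, Grade 2: drug hold | Total bilirubin | Improvement of the bilirubin elevation to Grade 1 or lower |
| 6.5.2.2.2, Grade 3-4: twice-weekly tests | Total bilirubin > 3 x ULN | AST/ALT at Grade 1 or baseline |

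Only the last row is mismatched.

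**2. The rule applied literally**

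- *Isolated hyperbilirubinemia.* Section 4.2.3 makes total bilirubin > 3 x ULN a DLT without any AST/ALT rise, so the protocol foresees this case. AST/ALT are already at Grade 1 or baseline, the release condition is true at onset, and the minimum duration of testing is zero.
- *Mixed elevation.* Testing may end when AST/ALT recover, whatever the bilirubin. Patients with hepatic metastases may enter with AST/ALT up to 5 x ULN (Section 5.1, criterion 10c), so for them the baseline condition can be reached sooner.

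**3. Whether another rule fills the gap**

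- *Steroid response at 3 to 5 days (6.5.2.2.2):* implies about one repeat test, not follow-up to recovery.
- *Follow-up after discontinuation (5.3.1) and continued observation after a related immediately reportable event (7.8.2.6):* no test frequency or bilirubin end point.
- *SAE follow-up to resolution (7.8.6):* serious events only; no frequency.
- *End of Treatment Visit (8.3):* optional, with timing "depending on ability to follow the patient and duration and severity of ongoing AEs".
- *Scheduled tests in Cohort 4:* bilirubin belongs to special chemistry ("Includes amylase, total and direct bilirubin, lipase"). Table 9 places it at "C1: D1, 22, C2 and beyond: D1, 22", before infusion. The Appendix 1 schedule adds screening and the End of Treatment Visit. Because study drug stops at this threshold, the pre-infusion draws may not take place.

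**4. Size**

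- Twice weekly: mean interval 7 / 2 = 3.5 days.
- Assumed bilirubin recovery of 2, 3 or 4 weeks: 2 x 2 = 4, 3 x 2 = 6 or 4 x 2 = 8 tests with a bilirubin end point.
- As written, isolated case: about 1 implied test.
- Nominal spacing of Cohort 4 scheduled draws, were they to continue: 22 - 1 = 21 days at the closest.

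**5. Reach**

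For the pembrolizumab combination, Section 2.3.1.1.2 states that "patients enrolled in these cohorts have completed combination treatment". That leaves mainly Cohort 4, at most 15 patients per dose level (Section 4.1.2). A DLT is fixed when the Section 4.2.3 threshold is crossed, so DLT counts do not depend on how long testing continues.

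**The case against.** The strongest reply is that this is a copying slip with little clinical consequence. Section 6.5.2 calls the rules general guidelines. The bullet sits under a bilirubin heading and asks for liver function testing, a term that Section 5.1 (criterion 15) uses for ALT/AST and bilirubin together. An investigator giving methylprednisolone 2 mg/kg/day for bilirubin is unlikely to stop testing because ALT is normal. An adverse event that forces discontinuation must be reported to the sponsor within 24 hours, and events are followed to the End of Treatment Visit or 28 days after the last dose. An assumed recovery of 2 to 4 weeks falls broadly within that period. Finally, the 21-day schedule belongs to patients still on treatment, so setting it against 3.5 days is inapt.

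Part of this stands. A careful clinician would probably keep testing, and harm is possible rather than shown. The 21-day spacing is not the schedule these patients would follow. That leaves them with less scheduled testing rather than more.

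The rest does not repair the rule. The bullet is written as an instruction, and the discretion it grants concerns frequency, not when to stop. Reporting an event does not schedule a blood test. The 28 days run from the last dose, not from the event. If the elevation is found at a Q3W pre-dose draw 21 days after that dose, 28 - 21 = 7 days remain, unless a later End of Treatment Visit extends the period. No section supplies a bilirubin end point.

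**Conclusion.** The concern holds. For Grade 3-4 bilirubin elevations the protocol ends its only close liver follow-up on the wrong analyte. In an isolated elevation it sets no minimum duration of testing. The error is in the text and rests on no assumption. The gap of roughly 1 test against 4 to 8 does rest on one: a recovery time of 2 to 4 weeks, which the documents do not give.

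The practical effect is small in numbers, and sample size, DLT counts and planned analyses are untouched. It is still an operative safety rule that is wrong as written and almost free to correct, so it should be corrected.

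**What to change.** In the Grade 3 block of Section 6.5.2.2.2, change the end of the monitoring bullet to: *until total bilirubin, and transaminases if elevated, have returned to Grade 1 or baseline*. Grade 4 then follows through its existing cross-reference. Keeping baseline as an alternative matters for patients with Gilbert's syndrome, who may enroll with total bilirubin above the usual limit (Section 5.1, criterion 10d). The clinical team may prefer a different recovery level. The transaminase bullet in 6.5.2.2.1 needs no change.

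The cost is a few words in one bullet and a few additional local blood tests in rare patients, now mainly in Cohort 4.
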